This study involves data from OCHIN's network of safety net clinics, 42 of which will be recruited for formal study participation. All EHR data from OCHIN clinics are stored at OCHIN. Each clinic has business use agreements with OCHIN to handle and manage PHI from their clinical data. EHR data will be linked using OCHIN's unique patient identification codes, in order to create clinic-level aggregate data and a limited data set.

All data sources will be linked into a secure relational database at OCHIN. The de-identification process replaces the original identifiers on sensitive or confidential fields with arbitrary pseudo-identifiers. Access to the "crosswalk" tables that contain mappings of original- to pseudo-identifiers is limited to authorized OCHIN staff; crosswalk tables will not be shared with OHSU or CHR. We will de-identify the following fields:

- Patient ID
- Provider ID
- Encounter ID

Data analysis will be conducted at OCHIN, OHSU, UNC, and WSU. If necessary, to share PHI, we will use a secure data transfer method (e.g., sFTP) with access limited to appropriate members of the research team. IRB and HIPAA approval will be obtained for all study steps. CHR, OHSU and OCHIN have expertise in high-

ASCEND: ApproacheS to CHC implEmeNtation of SDH data collection and action

quality data and secure management and project operations and multisite research collaborations. Data structures are typically designed to separate personal identifiers from other critical data, further enhancing protections.

CHR, OHSU, and OCHIN standards meet or exceed requirements for patient data safety established in the federal HIPAA guidelines. Data structures will derive from the data confidentiality, security, and privacy standards that CHR, OCHIN, and OHSU have in place to meet or exceed all current HIPAA requirements. Quality control will begin with real-time, inter-field checks in the data at OCHIN. Additional back-end checks (for missing data and logical inconsistencies) will be conducted to ensure the highest standards of data reliability. We will examine the distribution and measurement properties of variables before making final decisions about analyses.

10. Risks and Benefits

a. Risks to Subjects

The ASCEND study poses minimal risk. We do not anticipate any physical, psychological, social, legal or economic risks.

b. Potential Benefits to Subjects

Overall benefits: This research has the potential to provide valuable information on how best to support uptake of standardized collection of patients' SDH data using EHR-based tools, and integration of SDH data into DM / obesity risk management in CHCs.

Quantitative: Patients at the study CHCs will have no defined personal benefit from this project.

Qualitative: Care team members at the study CHCs will have no defined benefits from participating in this project. However, the intervention is designed to optimize identification and management of adult subjects with elevated DM risk. Some providers exposed to this potentially useful CDS may use it to improve their clinical care during the study or after.

11. Costs to Participants

CHC patients: There are no new costs to patients as a result of this study; however they will continue to pay for co-pays, routine treatment costs, etc. as part of normal care at their CHC.

CHC staff: There are no costs to staff as a result of this study; other than time spent during interviews and observations.

12. Compensation to Participants

ASCEND: ApproacheS to CHC implEmeNtation of SDH data collection and action

CHCs: During Year 1, the recruited CHCs (N=up to 12) will receive an impact fee in the amount of \$300 for participation in formative data collection.

CHC patients: None

CHC staff: During Years 1-4, CHC staff will receive a gift card in the amount of \$25 or \$50 for participation in the interviews and the card study (short de-identified provider survey).

Resources Available

No special resources or expertise are required to conduct this study.

13. Drugs or Devices

Not applicable.

14. Multi-Site Coordination

CHR will act as the coordinating center for this study. We will ensure that:

- All sites have the most current version of the protocol, consent document, and HIPAA authorization.
- All required approvals have been obtained at each site (including approval by the site's IRB of record).
- All modifications have been communicated to sites and approved (including approval by the site's IRB of record) before the modification is implemented.
- All engaged participating sites will safeguard data as required by local information security policies.
- All local site investigators conduct the study appropriately.
- All non-compliance with the study protocol or applicable requirements will be reported in accordance with local policy.
- Communication of problems, interim results, and study closure.

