- The quantitative team will collect baseline data from 6/24/16-12/31/17 for the 440 CHCs that share OCHIN's EHR. We will measure clinic-level SDH data collection rates as percentage of adult patients seen in 6/24/16-12/31/17 for whom patient-reported SDH data from the IOM's list are recorded, on a monthly basis. We will assess variation in rates of SDH data collection and identify clinic-level factors associated with this variation, using standard statistical methods. The distribution of the outcomes of interest and eligible population will be examined before selecting an analysis model; specific models will be refined iteratively, guided by the hypotheses and conceptual model.

Fine-tune the SDH Action Plan

- Results from the formative evaluation (semi-structured interview and baseline data analyses) will be used to fine-tune the SDH Action Plan.

Aim 2

Clinic Recruitment and Randomization

- CHCs will be recruited in two separate waves for the pragmatic trial. Wave 1 (wedges 1, 2, and 3) will be recruited prior to the start of wedge 1. Wave two (wedges 4,5,6) will be recruited roughly 1 year later, prior to the start of wedge 4. Each wave of CHCs will be block randomized by baseline rates of SDH data collection.

ASCEND: ApproacheS to CHC implEmeNtation of SDH data collection and action

Pragmatic, Stepped-wedge Trial

- The implementation support team will provide tailored implementation support for SDH data collection / action to each CHC's needs for six months (one wedge at a time).
- CHC Staff Baseline Survey: Using the 'Building Blocks of Primary Care' (BBPC) model, we will assess the study CHCs' baseline status of four foundational components/'building blocks': (1) Engaged leadership; (2) Data-driven improvement using EHRs; (3) Empanelment; and (4) Team-based care. The survey will be completed by project champion at each clinic. We will send a survey asking about the CHCs' structural characteristics (payment, staffing, etc.), external policies and incentives that might have an impact, and other potentially impactful organizational characteristics not identifiable in EHR data, OCHIN member records, or the other baseline data. This information will help us understand the impact adoption of SDH data collection / action.

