We will also use a generalized estimating equation (GEE) approach to assess factors associated with patients' acceptance of a resource to address an identified social need (see model specification below). Acceptance of help will be calculated using the proportion of patients who screened positive for one or more social need who accept a help to address that need. GEE produces a population average effect that accounts for group-level correlation and is appropriate for repeated or correlated observations. To account for the likely correlation between patients within a clinic, the model will include clustering at the clinic level. GEE takes into account the specified correlation structure while selecting the final parameter estimates and generally controls for clustering more effectively than using post-processing adjustment. We will test exchangeable and unstructured correlations structures and compare models using Quasi-Likelihood AIC (QIC) test. We will select the model with the lower QIC value. Using the

ASCEND: ApproacheS to CHC implEmeNtation of SDH data collection and action

preferred model, we will assess predictors of positive screening including screening domain, patient characteristics, encounter characteristics, and clinic characteristics.

$$Y_i \text{ Patient acceptance} = \beta_0 + \beta_1 X_i \text{ Screening domain} + \beta_2 X_i \text{ Patient characteristics} + \beta_3 X_i \text{ Encounter characteristics} + \beta_4 X_i \text{ Clinic characteristics} + \mu_i$$

To characterize variability in food insecurity and other social risk screening implementation before and during the COVID-19 pandemic, we will use a multilevel mixed-effects model to predict implementation of screening based on site, provider, patient, and visit characteristics. Variables will include urbanicity at the site level; profession at the provider level; race/ethnicity, age, and number of diet-related chronic conditions at the patient level; and location (in-person v. telehealth) at the visit level.

Qualitative data analysis plan

Data from each case will be 'merged' for analysis, then compared within and across clinics to confirm, expand on, or challenge each site's finding. Data collection and analysis will be parallel and iterative; analysis will begin at the end of the first wedge and continue as data from each wedge is collected. A grounded theory approach and immersion-crystallization process will be used to identify data themes and patterns.

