ASCEND STATISTICAL ANALYSIS PLAN

ASCEND: ApproacheS to CHC ImplEmeNtation of SDH
Data Collection and Action

[NCT03607617](#)

Version: November 18, 2022

ASCEND Statistical Analysis

Data source and trial design. OCHIN, Inc. is a non-profit health center-controlled network. Its members (109 CHC organizations, operating 593 clinic sites in 16 states, as of September 2018) share a single instance of the Epic EHR. This stepped-wedge trial included 31 CHCs recruited from OCHIN's member CHCs; they are located in California, Georgia, Massachusetts, Montana, Ohio, Oregon, Washington, and Wisconsin. Recruitment occurred in two waves (14 in spring 2018 and 17 in fall 2019) to ensure that no recruited clinics waited more than a year for the intervention. Each set of clinics was block-randomized to wedges 1-3 and 4-6, respectively. A stepped wedge trial was chosen as an effective design for when an intervention under study cannot be rolled out simultaneously for everyone yet allows all to eventually receive the intervention. Clinics were eligible to participate if they were interested in implementing or expanding social risk screening / referral activities. They had to commit to identifying staff members to serve as a Clinician Champion and / or Operational Champion for the project and allowing those staff to participate in intervention activities (≥ 2 hours / month interacting with the implementation support team).

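### The acceptance-of-help GEE may select an unstructured working correlation whose entries and QIC depend on the row order of patients within clinics

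*Protocol*

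**What the plan says.** Protocol section 6 (Aim 3) lists, among its further questions, what influences whether patients accept or refuse help with a social need. Section 7a gives the only quantitative model for this.

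- Outcome: "Acceptance of help will be calculated using the proportion of patients who screened positive for one or more social need" and who then accept help. The left side of the model equation is patient acceptance.
- Clustering: "To account for the likely correlation between patients within a clinic, the model will include clustering at the clinic level".
- Working correlation: "We will test exchangeable and unstructured correlations structures and compare models using Quasi-Likelihood AIC (QIC) test".
- Selection: "We will select the model with the lower QIC value".
- Use of the chosen model: "we will assess predictors of positive screening including screening domain", together with patient, encounter and clinic characteristics.

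The section gives no link function, no index that orders patients within a clinic, no limit on cluster size and no fallback if a structure fails to fit. It does not say which clinics enter. The SAP does not mention this GEE, so nothing there changes the rule.

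**The concern.** An unstructured working correlation suits data in which position 1, 2, 3 means the same thing in every cluster, such as scheduled visits. Here the cluster is the clinic and its members are patients. The seventh patient in one clinic has no counterpart in another, so the correlation between positions 3 and 7 describes nothing.

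Two consequences follow. The matrix, the coefficients and the QIC change when the file is re-sorted. And when clinics hold many patients relative to the number of clinics, the matrix cannot be estimated as a proper correlation matrix. At stake is which model, with which standard errors, supports the findings on acceptance of help.

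**Working it through.** The documents give no sample size, cluster size or power figure for this analysis, so there is nothing to reproduce. The check has four steps.

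**1. Dependence on order.** With K clinics and standardised residuals e, the moment estimate for positions j and k is r(j,k) = (1/K) Σ e(i,j)·e(i,k), summed over clinics i. Shuffling patients within each clinic changes which products enter r(j,k). The exchangeable estimate averages over all pairs within a clinic, so shuffling leaves it unchanged. This step needs no assumed figure.

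**2. Number of parameters.** An unstructured matrix for a largest clinic of m patients has m(m−1)/2 correlations; exchangeable has 1. Inputs:

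- K = 31 for the trial: "This stepped-wedge trial included 31 CHCs recruited from OCHIN's member CHCs".
- K = 440 if the 2016–17 network is meant: "The quantitative team will collect baseline data from 6/24/16-12/31/17 for the 440 CHCs that share OCHIN's EHR". K = 593 if all sites in the SAP's data source paragraph are meant.
- Trial sample: SAP, Outcome measures, gives 3,720 exclusions as 0.7% of the total. 3,720/0.007 ≈ 531,000 (496,000 to 572,000, allowing for rounding of 0.7%). Divided by 31, this is about 17,100 per clinic (16,000 to 18,500).

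The share of patients who enter the GEE is not given, so it is an assumption:

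| Assumed share | Average m | m(m−1)/2 |
|---|---|---|
| 10% | 1,714 | about 1.47 million |
| 1% | 171 | about 14,600 |
| 0.5% | 86 | about 3,600 |
| 0.2% | 34 | about 570 |
| 0.1% | 17 | about 140 |

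The average trial clinic reaches m = 31 at 31/17,143, or about 0.2% of its patients.

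**3. Positive definiteness.** Matrices were simulated with an assumed intraclass correlation of 0.05, 40% acceptance and equal clinics, 20 runs per setting. Number not positive definite:

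- K = 31: 0 of 20 at m = 10 and 20; 20 of 20 at m = 31, 50 and 100.
- K = 440: 0 of 20 at m = 50 and 200; 20 of 20 at m = 440 and 600.
- K = 593: 20 of 20 at m = 593 and 1,000.

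At every size the entries before and after re-sorting were essentially uncorrelated (−0.08 to 0.02).

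**4. Fitted models.** Logistic GEE fits used 31 clinics, one simulated data set per size and three row orders. The exchangeable fit was identical in all three orders.

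| m | Exchangeable QIC | Unstructured QIC, three orders | Exchangeable SEs (intercept, slope) | Unstructured SEs (intercept; slope) | Unstructured converged |
|---|---|---|---|---|---|
| 10 | 409.1 | 409.6, 409.4, 410.0 | 0.122, 0.081 | 0.109–0.114; 0.069–0.093 | yes |
| 20 | 827.4 | 827.9, 827.8, 827.0 | 0.093, 0.081 | 0.053–0.067; 0.046–0.056 | yes |
| 50 | 2055.3 | 2061.2, 2063.7, 2094.2 | 0.089, 0.050 | 0.005–0.006; 0.002–0.003 | no |
| 100 | 4132.3 | 4188.2, 4218.3, 4193.6 | 0.092, 0.033 | 0.001–0.002; 0.001 | no |

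At m = 20 the printed QIC changes its choice with row order alone. At m = 50 the slope was 0.232 under exchangeable and 0.283, 0.202 and 0.095 under the three unstructured orders.

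One caution on these values. The package (statsmodels) does not use the usual logistic weighting in its QIC penalty, so SAS, which the protocol names, would print other numbers. The order dependence does not rest on that penalty. The simplified criterion printed alongside QIC has a fixed penalty of 2 × 2 = 4. Removing it at m = 20 leaves 826.4 for exchangeable in every order, against 831.6 − 4 = 827.6, 831.4 − 4 = 827.4 and 830.5 − 4 = 826.5 for unstructured. A rerun on fresh simulated data with the usual penalty also gave choices that changed with row order.

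**The case against.** Several points on the other side have force.

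- A reader might infer that the analysis cannot be run at all. The documents do not support that. Exchangeable is one of the two named candidates, software may print a QIC for both, and the unstructured fits converged at m = 20 and below. What is missing is a valid comparison, not a usable model.
- The protocol keeps some freedom. The end of section 9 says that variables will be examined before analyses are finalised. That would allow a change, but it is general and leaves this rule standing.
- Neither the clinic set nor the number of patients per clinic is stated for this GEE. This stands, and it makes the positive-definiteness problem conditional. It does not touch the ordering problem, which holds for small clinics and for any number of clinics.
- Responses by screening domain within a patient would give a short, fixed index: 10 to 14 domains need 45 to 91 correlations. That would be workable, but the protocol says "the model will include clustering at the clinic level" and describes correlation between patients.
- GEE coefficients are consistent under a wrong working correlation if the mean model is right. True, but that is a property of many clusters. With 31 clinics the simulated coefficients and standard errors moved materially.
- The fits with implausibly small standard errors gave warnings, and in the table they had the higher QIC. They would probably be noticed. QIC is a weak safeguard, however: its penalty is built from the robust covariance, so a fit with falsely small standard errors is hardly penalised. In the rerun, some non-converged unstructured fits had the lower QIC.

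A reader might also infer that the plan names two competing dependent variables. The reference to positive screening is a wording slip. The opening sentence, the outcome definition and the equation all name acceptance, and having any positive screen cannot vary among patients who all screened positive.

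**Conclusion.** The rule is wrong as written. With patients clustered in clinics, an unstructured matrix has no meaning, and selecting it by QIC depends on file order. This follows from the protocol's text alone.

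The further problem, a matrix that is not positive definite with non-convergence or unreliable standard errors, arises generally once the largest clinic has at least as many patients as there are clinics. With the 31 trial clinics that is likely, since about 0.2% of an average clinic's patients would be enough. It rests on the derived figure of about 17,100 patients per clinic and an assumed share entering the model. In a network-wide analysis it would need several hundred patients in the largest clinic. The simulations illustrate the behaviour under assumed inputs and do not predict this trial's results.

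The importance is small. This is an additional analysis of associations. A reader should not carry the point over to the stepped-wedge comparison, which the SAP analyses with mixed models that do not use this rule.

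**What to change.** In Protocol section 7a, delete the unstructured option and the QIC selection. Specify a GEE for acceptance of help as a binary outcome with a logit link, an exchangeable working correlation by clinic, and robust standard errors clustered by clinic. Name the clinics that enter, and add a small-sample correction to the standard errors if they are only the 31 trial clinics; with several hundred clinics it would matter little. In the sentence that applies the chosen model, replace positive screening with acceptance of help.

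The cost is a few sentences. No new data are needed, and one model is fitted in place of two. The small-sample correction, if it applies, is an added setting in the same fit.

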ASCEND STATISTICAL ANALYSIS PLAN

ASCEND: ApproacheS to CHC ImplEmeNtation of SDH
Data Collection and Action

[NCT03607617](#)

Version: November 18, 2022

ASCEND Statistical Analysis

Data source and trial design. OCHIN, Inc. is a non-profit health center-controlled network. Its members (109 CHC organizations, operating 593 clinic sites in 16 states, as of September 2018) share a single instance of the Epic EHR. This stepped-wedge trial included 31 CHCs recruited from OCHIN's member CHCs; they are located in California, Georgia, Massachusetts, Montana, Ohio, Oregon, Washington, and Wisconsin. Recruitment occurred in two waves (14 in spring 2018 and 17 in fall 2019) to ensure that no recruited clinics waited more than a year for the intervention. Each set of clinics was block-randomized to wedges 1-3 and 4-6, respectively. A stepped wedge trial was chosen as an effective design for when an intervention under study cannot be rolled out simultaneously for everyone yet allows all to eventually receive the intervention. Clinics were eligible to participate if they were interested in implementing or expanding social risk screening / referral activities. They had to commit to identifying staff members to serve as a Clinician Champion and / or Operational Champion for the project and allowing those staff to participate in intervention activities (≥ 2 hours / month interacting with the implementation support team).

Intervention. The intervention details and conceptual frameworks underlying this study are previously described. In brief, study clinics received six months of technical assistance in the use of relevant EHR tools and practice coaching in how to use these tools in clinic workflows, both tailored to individual clinics' needs. (The relevant tools in the study clinics' shared Epic EHR supported: identifying patients due for social risk screening; customizing which patients were considered due; documenting and reviewing screening results; and ordering social service referrals.) An EHR trainer and a practice coach guided study clinics through a five-step implementation process: (1) secure leadership buy-in; (2) set goals; (3) develop workflows; (4) orient staff; and (5) implement and iterate. They met with clinic representatives 2-3 times monthly throughout a six-month intervention period, and tracked clinic progress through these steps. All meetings were conducted via video conferencing, a feature intended to enhance the intervention's potential scalability. The intervention was designed to address barriers to social risk screening / referral implementation identified in a prior pilot study (R18DK105463) and as reported in the literature. Prior evidence suggested that each intervention component – practice coaching / facilitation, technical assistance, interdisciplinary support teams, tailored support, staff training, feedback data, goal identification, leadership engagement, peer-to-peer learning, orientation materials, and 'how-to' guides – had the potential to effectively support practice changes in primary care settings.

Study period. The study period was March 2018 through December 2021 and included six 6-month intervention wedges. The first (wedge 1) 6-month intervention began in September 2018, and the last (wedge 6) began January 2021. This allowed for at least six months of data collection before each wedge started, and after the last wedge ended. Thus, all months prior to the 6-month intervention periods were considered 'pre-intervention,' the six months of the intervention were the 'intervention phase,' and all months from the intervention period's end through December 2021 were 'post-intervention.' Of note, wedge 4 began in February 2020 as the COVID-19 pandemic began impacting care delivery in the study clinics.

Outcome measures. Patient- and encounter-level data were aggregated to the clinic level, limited to persons 18 years or older. Patients seen only for COVID-19 vaccination / testing were excluded (n=3,720; 0.7% of total study sample). Primary analyses centered on social risk screening and related referrals, and

included two outcome measures. The first was the monthly clinic rate of social risk screening, measured as the number of patients with documented social risk screening among those with a face-to-face clinical encounter in the measurement period (excluding those only for COVID testing / vaccination). Domains of social risk screening included child / family care insecurity, education, employment, financial strain, food insecurity, health insurance, health literacy, housing instability, inadequate physical activity, relationship safety, social isolation, stress, transportation needs, and utilities insecurity. The second outcome was the monthly clinic rate of provision of social risk-related referrals, measured as the number of patients with a documented referral among all patients seen in the measurement period (regardless of whether social risk screening was documented). This outcome included referrals internal (e.g., to a social worker) or external to the clinic (e.g., to housing services). As the EHR enabled documenting when patients declined to answer social risk screening questions or declined offered referrals, documented declinations were considered to indicate that screening or referral actions were taken, and included in the numerators described above.

Given the known association between social risks and diabetes outcomes, secondary analyses assessed intervention impacts on diabetes control and receipt of relevant diabetes care. Patients with an encounter during the study period and established diabetes prior to the second month of their clinic's baseline period comprised this subpopulation cohort (excluding pregnant women). Guideline-concordant diabetes-related care was considered monthly for this cohort and included whether patients were up to date on receipt of their (1) annual lipid panel and (2) biannual hemoglobin A1c (HbA1c) screening. Three diabetes control measures were assessed monthly, among patients screened that month: (1) blood pressure (BP; <130/80 mmHg), (2) HbA1c (<7.0%), and (3) low-density lipoprotein (LDL; <100 mg/dL).

Baseline covariates. The baseline period was defined as the six months before each clinic's wedge began. Analyses accounted for clinic-level baseline measures: number of years since the clinic began using their current EHR; whether the clinic conducted screening at or above the 50th percentile for all study clinics (to capture prior experience with such screening), and patient characteristics aggregated to the clinic level. We also accounted for whether the clinic was concurrently involved in the Centers for Medicare and Medicaid Services (CMS) Innovation Center's Accountable Health Communities (AHC) Model, a large national demonstration project targeting implementation of social risk screening and navigation services. Participants involved in this demonstration received modest financial incentives but only minimal implementation support.

Statistical analysis. Clinic-level outcomes were monthly from March 2018 through December 2021 (totaling 1,384 monthly time points across 31 clinics). Generalized Linear Mixed Models (GLMMs) were used to assess intervention effect by comparing outcomes during time periods in clinics which had versus had not yet participated in the intervention. GLMMs were used to account for a general time trend and flexibly model the intervention effect over time post-intervention. Negative binomial mixed-effects modeling was used to evaluate the primary outcomes; mixed-effects linear regression was used to evaluate secondary outcomes. Each GLMM fit flexible time effects by treating time as a categorical variable and included random effects for clinics, adjusted for baseline covariates, and utilized robust standard errors. Average differences are reported comparing the pre-intervention period to (1) the six-month intervention period and (2) the post-intervention period. Rate ratios (RR) for the primary

outcomes, rate differences for the secondary outcomes, and corresponding 95% confidence intervals (CI) are reported. A more detailed description of the GLMM model is provided by:

The general model is:

$$\log(Y_{it} | b_i) = \beta_0 + \beta_1 t + \beta_2 I_{it}(t - s_i) + \beta_3 Z_i + \theta C + b_i + \log(e_{it})$$

Y_{it} is the number of patients in practice i whom had any SDH data collected during period t .

t is a categorical variable denoting the observation month for t in $(0, 1, \dots, 46)$, where $t = 0$ is the baseline month.

I_{it} is an indicator variable where $I_{it} = 1$ if practice i has been assigned to the intervention at period t , and $I_{it} = 0$ otherwise.

s_i is the period (month) when the intervention begins for practice i .

Z_i is a practice-level term to denote baseline rates of SDH data collection, where $Z_i = 1$ if practice i has high rate of SDH data collection (above 50th percentile) and $Z_i = 0$ if low rate (below 50th percentile).

C is a matrix of potential confounders with corresponding vector of coefficients θ .

b_i denotes a random effect term for practice i with mean 0 and variance σ_b^2 .

E_{it} is the number of patients seen in the practice during the observation month t in practice i and the $\log(E_{it})$ term is considered the 'offset' in the Poisson regression model.

The estimation via the above model takes into account the general time trend, and allows for the intervention effect to grow over time following intervention implementation. The model estimates the intervention effect with the within-site difference between SDH collection rates pre- and post-intervention, averaging across practices and accounting for possible secular trends which might confound with the timing of the intervention implementation.

Note on protocol deviation. The GLMM model specifications written at the time of trial registration were based on the then-flagship paper for analysis of stepped-wedge clinic-randomized trials. This approach utilized continuous variables for modelling the general time-trend of the outcomes without intervention, and estimating the added intervention effect that accrues over time following intervention initiation. This approach originally provided an estimate for the intervention effect that appears in the first time period (month) of intervention. Since trial registration, advances have been made in the analysis of such study designs that improve ability to estimate intervention effects. We updated the GLMM specifications in these analyses to reflect these advances by using the more flexible, categorical time variables. Additionally, we dropped the stand-alone estimator for intervention effect in the first month of intervention as it is unlikely the effect was immediate and constant; instead this estimator was absorbed into the categorized estimator for added intervention effects. Ultimately, these modifications resulted in changes to our reported outcomes. Instead of reporting intervention effect in the first month of intervention and the added intervention effect beyond the first month until study end, we report the average intervention effect for the 6 months of hands-on intervention and for the post-intervention period. We only report estimates from the updated models in the main results. We provide a comparison of estimates using both the original and updated models.
